**A11002001**

**29 May 2025**

## **Study Protocol and Statistical Analysis Plan**

This multicentre, prospective, double-blind, two-arm, parallel-group randomized clinical trial was conducted between January 2022 and June 2024 to evaluate the efficacy of a topical probiotic formulation in a soybean concentrate compared with placebo in the treatment of diabetic foot ulcers (DFUs) (ClinicalTrials.gov Identifier: A11002001). Participants were randomized to receive twice-daily application of either investigational product (bottle A) or placebo (bottle B), both administered directly to the wound in addition to standard care. The contents of each bottle were prepared off-site, and both investigators and participants were blinded to treatment allocation.

The trial was conducted across three hospitals in Taiwan—Dalin Tzu Chi Hospital (Chiayi County), Taichung Tzu Chi Hospital (Taichung City), and Hualien Tzu Chi Hospital (Hualien City)—by three senior plastic surgeons, each with expertise in DFU wound management. The study was conducted in accordance with the principles of the Declaration of Helsinki (2013) and Good Clinical Practice guidelines. Ethics approval was obtained from the Institutional Review Boards of each participating centre. All participants provided written informed consent prior to enrolment. The trial was conducted and reported in accordance with the Consolidated Standards of Reporting Trials (CONSORT) guidelines.

## **Study Population**

Eligible participants were adults with a diagnosis of diabetes mellitus and a non-healing DFU measuring greater than 1 cm^2 in area, without exposed bone or tendon. Full inclusion and exclusion criteria are shown in Table 1.

## **Randomization and Intervention**

Block randomization in blocks of 8 was used to assign participants to 1 of 2 groups: Group 1 received bottle A (topical probiotic in soybean concentrate) and Group 2 received bottle B (placebo). Both groups received secondary dressing with standard wound care with wet-to-dry dressings. The assigned topical treatment was applied directly to the ulcer twice daily throughout the treatment phase.

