## **Outcomes and Data Collection**

Baseline demographic data, medical history, comorbidities, current treatments, and wound characteristics were recorded at enrolment. Participants were evaluated weekly or biweekly for up to 24 weeks or until complete wound healing, whichever occurred first. At each visit, wound surface areas were measured and documented using standardized digital photography. Adverse events were assessed and documented at each visit. Debridement, when necessary, was performed as part of routine clinical care and recorded.

The **primary outcome** was the proportion of wounds achieving complete healing within 24 weeks. Complete wound healing was defined as full re-epithelialization without drainage or dressing requirements. Wound healing was assessed jointly by the treating plastic surgeon and wound care nurse. Due to resource constraints, independent blinded assessors were not employed.

**Secondary outcomes** included percentage reduction in wound area, wound recurrence rates, incidence and nature of adverse events, and the need for additional surgical intervention. Participants who achieved wound healing were followed at 2- and 12-weeks post-healing to monitor for recurrence or complications.

Unblinding of treatment allocation was permitted only in the case of a serious adverse event (SAE) in which treatment knowledge was required for patient safety. All unblinding events were documented and reviewed by the data monitoring committee. Otherwise, treatment codes remained concealed until study completion.

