## **Statistics**

All analyses were performed using IBM® SPSS® Statistics V25. Continuous variables were summarized using means and standard deviations. Categorical variables were expressed as frequencies and percentages. Paired *t* tests were used to evaluate differences in continuous variables. Chi-square ( $\chi^2$ ) tests were applied for comparisons of categorical variables. Survival outcomes were assessed using Kaplan–Meier analysis and Cox proportional hazards regression modelling. All tests were two-sided, and *p* values  $< 0.05$  were considered statistically significant.

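### No hospital stratum is stated for the blocks of 8 and no analysis accounts for hospital, although three hospitals, apparently one surgeon each, treat the wounds and judge healing

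*Combined protocol and SAP*

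**What the plan says.** Under Randomization and Intervention the rule is "Block randomization in blocks of 8 was used to assign participants to 1 of 2 groups". No stratification factor, number of lists or place of list generation follows.

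The opening section says "The trial was conducted across three hospitals in Taiwan" and that the work was done "by three senior plastic surgeons, each with expertise in DFU wound management". It does not say which surgeon worked where. It also says that "both investigators and participants were blinded to treatment allocation".

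Under Outcomes and Data Collection, "The primary outcome was the proportion of wounds achieving complete healing within 24 weeks". On who decides that a wound has healed: "Wound healing was assessed jointly by the treating plastic surgeon and wound care nurse". The section adds: "Due to resource constraints, independent blinded assessors were not employed".

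Under Statistics, chi-square "tests were applied for comparisons of categorical variables". Kaplan-Meier and Cox methods are listed for survival outcomes, without covariates or strata. No test is tied by name to the primary outcome, but chi-square is the only listed test that fits a proportion. Hospital appears in no analysis.

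**The concern.** Hospital may carry several influences on the primary outcome at once: case mix, local care, the surgeon, and the threshold at which a wound is called healed. Part of that threshold is whether a dressing is still needed, which is a judgement. That the treating surgeon is an assessor is stated. That each hospital had one surgeon is an inference from three and three.

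The allocation sentence allows two readings, and each leaves a weakness.

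- **One list over all hospitals.** Blocks of 8 balance the arms overall but not within a hospital. If hospitals heal at different rates, a chance difference in hospital mix moves the observed difference between arms, and an unadjusted test treats that movement as noise.
- **One list per hospital.** Mix is nearly balanced by design, but a chi-square that ignores the strata uses too large a variance and gives back part of the benefit.

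At stake are the precision of the primary comparison and the credibility of this one result. The secondary outcomes are exposed in the same way.

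**Working it through.** **Inputs from the plan.** Two arms, blocks of 8, three hospitals, a binary primary outcome, chi-square for categorical data, two-sided 5% level. The plan gives no sample size, power or healing rate, so it has no figure of its own to reproduce.

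**Assumptions, none from the plan.** Total N of 48 to 200, equal expected enrolment per hospital, and healing by hospital of 30/50/70% (strong differences) or 40/50/60% (mild).

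**Step 1: variance between hospitals.** The mean rate is 0.50 in both cases, so the total outcome variance is 0.50 × 0.50 = 0.25.

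- Strong: (0.2² + 0 + 0.2²)/3 = 0.0267, which is 0.0267/0.25 = 11% of the total.
- Mild: (0.1² + 0 + 0.1²)/3 = 0.0067, about 3% of the total.

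**Step 2: single list.** With N/2 per arm, the shift in the arm difference due to hospital mix alone has mean 0 and SD = √(between-hospital variance × 4/N). The ordinary standard error of the arm difference is √(0.25 × 4/N).

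| N | Shift SD, 30/50/70% | Shift SD, 40/50/60% | Standard error |
|---|---|---|---|
| 48 | 4.7 points | 2.4 | 14.4 |
| 80 | 3.7 | 1.8 | 11.2 |
| 120 | 3.0 | 1.5 | 9.1 |
| 200 | 2.3 | 1.2 | 7.1 |

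Simulation with actual blocks of 8 agrees. Under 30/50/70% the SDs are 4.7, 3.7 and 3.0 points at N = 48, 80 and 120, and the shift exceeds 5 points in 27%, 17% and 9% of trials. Under 40/50/60% it does so in 3%, 0.6% and 0.1%.

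**Step 3: per-hospital lists in blocks of 8.** Under 30/50/70% the shift SD falls to 1.5, 0.9 and 0.6 points at N = 48, 80 and 120. Shifts above 5 points occur in 0.1% of trials or fewer.

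**Step 4: false-positive rate.**

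- *Single list, chi-square:* 4.9 to 5.6% in simulations at N = 60, 120 and 200, and 5.8% in one at N = 80. The excess at N = 80 is not a hospital effect. Two arms of 40 with a common 50% healing rate and no hospital differences give an exact rate of 5.7% for the uncorrected chi-square, because the data are discrete.
- *Per-hospital lists, chi-square:* with perfect balance, the true variance is 1 − 0.0267/0.25 = 0.893 of what the test assumes. The critical value becomes 1.96/√0.893 = 2.07, a rate of about 3.8%. Simulation, with unfinished blocks, gives about 4.1 to 4.5% under 30/50/70% and roughly nominal rates under 40/50/60%.
- *Per-hospital lists, Cochran-Mantel-Haenszel (CMH):* 4.6 to 5.2% under 30/50/70%.

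**Step 5: power.** For a true 25-point difference under 30/50/70%:

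| N | Single list, chi-square | Per-hospital lists, chi-square | Per-hospital lists, CMH |
|---|---|---|---|
| 80 | 63.8% | 64.8% | 66.9% |
| 120 | 80.0% | 81.8% | 83.8% |

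At N = 48 there is no material change.

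A second set of simulations (log odds ratio 1.0; 6,000 trials per setting, Monte Carlo error about 0.6 points) separates the test from the list:

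| N, rates | Single, chi-square | Single, CMH | Per-hospital, CMH |
|---|---|---|---|
| 60, 30/50/70% | 39.5% | 40.8% | 42.0% |
| 120, 30/50/70% | 66.8% | 69.7% | 70.8% |
| 200, 30/50/70% | 87.4% | 90.2% | 90.1% |
| 60, 40/50/60% | 43.4% | 42.9% | 44.7% |
| 120, 40/50/60% | 72.6% | 72.8% | 74.1% |

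With strong hospital differences at N = 120 and 200, most of the gain comes from the stratified test and so needs no change to the lists. With mild differences the test alone gains nothing visible, and at N = 60 it may lose slightly.

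**The case against.** The strongest reply is that the plan is silent on strata and does not exclude them. Separate lists in blocks of 8 fit the same sentence and would nearly remove the imbalance. A reader might infer that randomisation was not stratified; the text does not establish that. This stands, and it is why both readings are worked through.

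A reader might also infer that hospital mix biases the primary result. It does not. The shift averages zero over randomisations and is part of the variation the chi-square already covers. Even under strong differences at N = 80 its SD is 3.7 points against a standard error of 11.2. Investigators are stated to be blinded, so a surgeon's own healing threshold applies to both arms. What remains is a loss of precision and one realised estimate that may be off by a few points for an avoidable reason.

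The link from hospital to outcome is assumed. No healing rates by hospital are given, and 30/50/70% is a wide spread: the odds ratio between best and worst is (0.7/0.3)/(0.3/0.7) = 5.4. That also stands, so the mild case is shown beside it.

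A further tempting reading is that fixed blocks of 8 let staff foresee allocations. Someone who knew the length and saw every letter at one hospital with its own list would know on average 4/5 + 4/5 = 1.6 of 8 letters, or 20%, with certainty. But the plan does not say that the length was disclosed, and a bottle letter is not the treatment. Varying the length over 4, 8 and 12 cuts certain letters to about 2.5% yet barely changes best-guess accuracy (66.6% to 65.7%). This does not carry the point.

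**Conclusion.** The point holds in a limited form. Hospital is a plausible predictor of the primary outcome, and the plan as written accounts for it neither in a stated allocation stratum nor in a stated analysis. Under a single list the cost is a chance shift in this trial's estimate, with an SD of about 3.7 points (30/50/70%) or 1.8 points (40/50/60%) at N = 80, and some lost precision. Under per-hospital lists the cost is a test that is slightly conservative when hospitals differ strongly.

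There is no average bias and no material type I inflation. Moving from a single list with chi-square to per-hospital lists with CMH gains about 3 to 4 points of power at N = 80 to 120 under strong hospital differences, and little under mild ones. All sizes rest on assumed N, equal enrolment and assumed healing rates. One surgeon per hospital, and chi-square as the primary test, are inferences from the text, though well-supported ones.

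**What to change.** - **Statistics.** Compare the proportion healed with a CMH test stratified by hospital, and stratify the Cox model for time to healing by hospital. Label both post hoc unless they were prespecified before unblinding.
- **Reporting.** Tabulate arm by hospital, so that readers can see the imbalance that actually occurred.
- **Randomization and Intervention.** State whether there was one list or one per hospital.
- **Design.** Stratifying the blocks by hospital was the better rule. The plan says the trial ran from January 2022 to June 2024, so this can be applied only if allocation is in fact still open; otherwise it is a lesson for the next trial.

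The analysis and reporting changes need a few lines of text and a re-run of the analysis, with no extra patients, visits or staff. There are two small downsides. With small N and weak hospital effects the stratified test can lose a little power. Per-hospital lists leave up to three unfinished blocks, so overall arm sizes can differ slightly more.

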## **Outcomes and Data Collection**

Baseline demographic data, medical history, comorbidities, current treatments, and wound characteristics were recorded at enrolment. Participants were evaluated weekly or biweekly for up to 24 weeks or until complete wound healing, whichever occurred first. At each visit, wound surface areas were measured and documented using standardized digital photography. Adverse events were assessed and documented at each visit. Debridement, when necessary, was performed as part of routine clinical care and recorded.

The **primary outcome** was the proportion of wounds achieving complete healing within 24 weeks. Complete wound healing was defined as full re-epithelialization without drainage or dressing requirements. Wound healing was assessed jointly by the treating plastic surgeon and wound care nurse. Due to resource constraints, independent blinded assessors were not employed.

**Secondary outcomes** included percentage reduction in wound area, wound recurrence rates, incidence and nature of adverse events, and the need for additional surgical intervention. Participants who achieved wound healing were followed at 2- and 12-weeks post-healing to monitor for recurrence or complications.

Unblinding of treatment allocation was permitted only in the case of a serious adverse event (SAE) in which treatment knowledge was required for patient safety. All unblinding events were documented and reviewed by the data monitoring committee. Otherwise, treatment codes remained concealed until study completion.

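### Adverse-event observation time depends on healing, so crude incidence can differ between arms at equal weekly risk, in a direction set by which visits count

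*Combined protocol and SAP*

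**What the plan says.** Under Outcomes and Data Collection, "Participants were evaluated weekly or biweekly for up to 24 weeks or until complete wound healing, whichever occurred first". The same section states "Adverse events were assessed and documented at each visit" and lists "incidence and nature of adverse events" among the secondary outcomes. It adds: "Participants who achieved wound healing were followed at 2- and 12-weeks post-healing to monitor for recurrence or complications". No visit after week 24 is described for participants who have not healed. The section does not say whether events found at the two post-healing visits count towards adverse-event incidence.

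Under Statistics, "Categorical variables were expressed as frequencies and percentages", and chi-square "tests were applied for comparisons of categorical variables". The section also says "Survival outcomes were assessed using Kaplan–Meier analysis and Cox proportional hazards regression modelling", without saying which outcomes these are. It gives no adverse-event window, denominator or rate per unit of time.

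**The concern.** A comparison of crude percentages is a like-for-like comparison of risk only if both arms are watched for about the same time. Here the period of regular visits ends when the wound heals. If the product speeds healing, its arm has less time under regular visits and a larger share of participants on the sparser post-healing schedule. Participants who heal late may be followed past week 24, when unhealed participants have no stated visits.

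Two arms with the same weekly risk can therefore show different percentages. A real difference in weekly risk can also be masked or exaggerated. Because the documents do not say which visits count, a reader of the results could not tell which way the distortion runs.

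**Working it through.** **Inputs from the documents.** Regular visits to healing or week 24; post-healing visits at 2 and 12 weeks for healers only. The documents give no healing rate, adverse-event rate or sample size, so there is no figure of theirs to reproduce.

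**Assumptions.** Healing by week 24 of p = 35% in one arm and 60% in the other. The same weekly hazard L of a first adverse event in both arms, 0.01 or 0.02. Capture either stops at healing (c = 0) or is complete for 12 weeks after it (c = 12). Three patterns of healing time: constant hazard, uniform over weeks 4–24, uniform over weeks 12–24.

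**Constant healing hazard.**
- h = −ln(1 − p)/24, which is 0.01795 at 35% and 0.03818 at 60%.
- Mean time under regular visits = p/h: 0.35/0.01795 = 19.5 weeks and 0.60/0.03818 = 15.7 weeks.
- Incidence with c = 0 is L/(L+h) × (1 − exp(−24(L+h))). At L = 0.01: 0.3578 × 0.4887 = 17.5% and 0.2076 × 0.6854 = 14.2%.
- With c = 12, add h/(L+h) × (1 − exp(−24(L+h))) × (1 − exp(−12L)). At L = 0.01: 17.5% + 0.3138 × 0.1131 = 21.0% and 14.2% + 0.5431 × 0.1131 = 20.4%.

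**Uniform healing from week a to week 24.**
- m = (exp(−aL) − exp(−24L)) / (L(24 − a)).
- Incidence = 1 − p·m·exp(−cL) − (1 − p)·exp(−24L).
- Example with a = 12, L = 0.02, c = 12: m = (0.7866 − 0.6188)/0.24 = 0.6994, and m × 0.7866 = 0.5501. At 35%: 1 − 0.35 × 0.5501 − 0.65 × 0.6188 = 40.5%. At 60%: 1 − 0.60 × 0.5501 − 0.40 × 0.6188 = 42.2%.

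**Results** (35% arm vs 60% arm; gap is the faster-healing arm minus the other, from the rounded percentages):

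| Healing time | Weekly hazard | Capture to healing | Gap | Capture to 12 weeks after | Gap |
|---|---|---|---|---|---|
| Constant hazard | 1% | 17.5 vs 14.2 | −3.3 | 21.0 vs 20.4 | −0.6 |
| Constant hazard | 2% | 31.5 vs 25.9 | −5.6 | 37.5 vs 36.4 | −1.1 |
| Uniform, weeks 4–24 | 1% | 18.4 vs 16.3 | −2.1 | 21.8 vs 22.2 | +0.4 |
| Uniform, weeks 4–24 | 2% | 33.1 vs 29.6 | −3.5 | 38.8 vs 39.3 | +0.5 |
| Uniform, weeks 12–24 | 1% | 19.6 vs 18.4 | −1.2 | 22.9 vs 24.1 | +1.2 |
| Uniform, weeks 12–24 | 2% | 35.3 vs 33.3 | −2.0 | 40.5 vs 42.2 | +1.7 |

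**Why the sign changes.** With uniform healing over weeks 12–24, healers heal at week 18 on average and are followed to week 18 + 12 = 30. Non-healers stop at 24. Over weeks 4–24 the healers' average is 14 + 12 = 26, again more than 24.

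**What could be masked.** With capture to healing and constant healing hazards, I solved for the weekly hazard in the faster-healing arm that gives the same crude percentage as the other arm. It is about 26% higher when the other arm has 1% per week, and about 28% higher at 2%.

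**Check of the remedy.** Divide first events by the time at risk up to the first event or the end of observation, (1 − exp(−24(L+h)))/(L+h). At L = 0.02 with constant healing hazards, per 100 participants: 31.5 events in 1,575 weeks and 25.9 events in 1,293 weeks. Both are 2.0 per 100 participant-weeks, so the artefact is gone.

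**The case against.** The best counter-argument is that the post-healing visits largely close the gap. Adverse events are recorded at each visit, those visits look for complications, and an event that began between visits can be reported at the next one. If every such event counts, the gap is 1.7 points or less in either direction. That stands as a limit on size. It is also the optimistic bound, because two visits in 12 weeks are sparser than the regular schedule and the plan does not say that their events enter the incidence.

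A constant healing hazard puts the most healing in the earliest weeks, which is the pattern most favourable to the concern; later healing gives smaller gaps. That stands too, and is why the range is given.

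A reader might infer that the faster-healing arm will always look safer. The documents do not support this: with later healing and full post-healing capture the sign reverses. A reader might also infer that the plan commits to a chi-square test of adverse events and will base a safety claim on it. It does neither. The chi-square sentence is general, Kaplan–Meier and Cox are not excluded for adverse events, and no safety hypothesis or margin is stated.

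Finally, crude cumulative incidence is a legitimate description: if faster healing shortens exposure and so reduces total events, that is a real consequence of treatment. This is a reason to keep the crude figures beside a rate, not to report them alone.

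**Conclusion.** The concern holds with a conditional direction. Adverse-event observation depends on healing, and the plan specifies nothing that accounts for it. At equal weekly risk of 1% to 2% and assumed healing of 60% versus 35%, crude incidence in the faster-healing arm is 1.2 to 5.6 points lower if only events up to healing count. If all events to 12 weeks after healing count, it lies between 1.1 points lower and 1.7 points higher. Both size and sign depend on the window and on when healing happens, and every rate used is an assumption. The point affects a secondary safety outcome, not the primary analysis. It should be corrected because the correction is cheap and the crude comparison cannot be interpreted without it.

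**What to change.** For events from first application to healing or week 24, whichever is first, add one of two analyses by arm:
- events per 100 participant-weeks, with a rate ratio and 95% CI; or
- time to first event, censored at the end of that window.

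Match numerator to denominator: first events over time to first event, or all events over all observed time with a variance that allows for repeat events. Tabulate events after healing separately. State which visits feed each table. Keep the crude percentages as description, and do not use their chi-square test as the safety comparison.

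The cost is one more safety table, built from event and visit dates that visit-based recording should already supply, plus a constant-rate assumption for the rate ratio. The rate answers the question of risk during treatment, not total adverse-event burden. A common 24-week window from randomization would address total burden, but the stated schedule supports it only in part: a participant who heals before week 12 has a last visit, 12 weeks later, before week 24. The difference between weekly and biweekly visits also remains, so the number of visits per arm is worth reporting alongside.

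### Participants are randomised but the primary outcome counts wounds, with no stated allowance for clustering; if some participants contributed several correlated ulcers, an ordinary chi-square would give too small a p value

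*Combined protocol and SAP*

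**What the plan says.** Under Randomization and Intervention, the unit of allocation is the person: "Block randomization in blocks of 8 was used to assign participants to 1 of 2 groups". Under Outcomes and Data Collection, the unit of the primary outcome is the wound: "the proportion of wounds achieving complete healing within 24 weeks". Under Statistics, chi-square "tests were applied for comparisons of categorical variables". That sentence does not name the primary outcome, but healed versus not healed is a categorical variable and no other test for such variables is given. Kaplan–Meier and Cox methods are listed for survival outcomes without a stated unit. No mixed model, GEE or robust variance is mentioned. "All tests were two-sided", with a 0.05 threshold.

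On ulcers per participant, the wording is singular. Study Population asks for "a non-healing DFU measuring greater than 1 cm" squared in area. Randomization and Intervention says "The assigned topical treatment was applied directly to the ulcer twice daily". Outcomes and Data Collection ends a participant's evaluation at healing or at 24 weeks, and dates the two post-healing visits from a participant's healing. Study Population refers to Table 1 for the full eligibility criteria. That table is not in the text available for review.

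**The concern.** The outcome definition and the randomisation use different units, and the available text does not say that the two coincide. All ulcers on one person receive the same assigned bottle and share that person's circulation, glycaemic control and care, so their healing is likely to be positively correlated. A chi-square test on wounds treats each wound as an independent observation. If several wounds per person were counted, it would understate the variance of the difference in healing proportions, and the primary comparison would reject a true null hypothesis more often than 5% of the time. The wound denominator would also give more weight to participants with more ulcers. A Cox model on wounds without a clustering term has the same variance problem.

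**Working it through.** The documents state no sample size, healing rate, wound count or ICC, so there is no figure of the plan's own to reproduce. The check asks how much the wording could matter.

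**Inputs from the documents**
- Unit randomised: participant (Randomization and Intervention).
- Unit of the primary outcome: wound (Outcomes and Data Collection).
- Test: chi-square, two-sided, 0.05 (Statistics). Its use for the primary outcome is inferred.

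**Assumed inputs, not in the documents**
- A share f of participants has two ulcers and the rest have one.
- The within-person ICC lies between 0.1 and 0.8.

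**Step 1: design effect.** With m ulcers per participant, D = 1 + ICC × (Σm²/Σm − 1). Here Σm² is proportional to 1 + 3f and Σm to 1 + f, so D = 1 + ICC × 2f/(1 + f).

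At ICC 0.5:
- f = 0.01: D = 1 + 0.5 × 0.02/1.01 = 1.010
- f = 0.10: D = 1 + 0.5 × 0.2/1.1 = 1.091
- f = 0.20: D = 1 + 0.5 × 0.4/1.2 = 1.167
- f = 0.50: D = 1 + 0.5 × 1.0/1.5 = 1.333

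**Step 2: actual type I error of the unadjusted test.** This is 2 × [1 − Φ(1.96/√D)].

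| Share with two ulcers | ICC 0.1 | ICC 0.3 | ICC 0.5 | ICC 0.8 |
|---|---|---|---|---|
| 0% | 5.0% | 5.0% | 5.0% | 5.0% |
| 1% | 5.0% | 5.1% | 5.1% | 5.2% |
| 10% | 5.2% | 5.6% | 6.1% | 6.7% |
| 20% | 5.4% | 6.2% | 7.0% | 8.2% |
| 50% | 5.8% | 7.4% | 9.0% | 11.4% |

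At ICC 0 every entry is 5.0%, whatever the share.

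**Step 3: effect on a reported p value.** Dividing the test statistic by √D at ICC 0.5, an unadjusted p of 0.040 becomes 0.041 (1% with two ulcers), 0.049 (10%), 0.057 (20%) or 0.075 (50%).

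**Step 4: simulation.** The unadjusted test was simulated 40,000 times per setting, with an assumed healing rate of 50% and 200 participants per arm. The rejection rate was 5.1% with no second ulcers. At ICC 0.5 it was 6.1%, 7.1% and 9.3% for shares of 10%, 20% and 50%. This agrees with the formula. At 40 and 80 per arm the rates scatter around it because the test is discrete: with no second ulcers they were 5.8% and 4.6%.

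**The case against.** The strongest objection is that the triggering condition is not shown and most of the text points away from it. Eligibility and treatment are written for a single ulcer. Follow-up ends at one healing event per participant, and the post-healing visits run from one date per participant. Those rules are hard to apply to a person with two study ulcers healing at different times. Nothing says that several ulcers per person could be enrolled or counted, and the word for wounds in the primary outcome may simply be loose. This stands: one ulcer each is the more natural reading.

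It is also fair that an ulcer-number rule would normally sit among the full criteria in Table 1. Because that table is not in the text available for review, the plan cannot be said to lack such a rule.

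A reader might infer from the wound denominator that the primary p value is in fact too small, or that one second ulcer anywhere would make it so to a material degree. The documents support neither. With one ulcer each there is no inflation. Inflation also needs positive within-person correlation, and with 1% of participants having two ulcers it is negligible.

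The objection does not remove the mismatch of units. Singular eligibility wording sets a minimum. It does not exclude a second ulcer or say which ulcer would count.

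**Conclusion.** The point holds as a conditional one. The primary outcome is worded in a different unit from the randomisation, and no method for correlated wounds is stated. Whether this affects the result depends on two facts that the documents do not give: whether anyone contributed more than one ulcer, and how strongly healing is correlated within a person. If each participant contributed one ulcer, the effect is nil and only the wording needs to change. Otherwise, at an assumed ICC of 0.5, the type I error ranges from about 5.1% (1% of participants with two ulcers) to 9.0% (50%). Given the singular wording, the low shares are the more plausible part of that range. The calculation also assumes that chi-square is the primary test and that nobody contributed more than two ulcers. It is worth correcting because the correction is cheap and sound under either reading.

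**What to change.** State the primary outcome as the proportion of randomised participants whose study ulcer healed completely within 24 weeks. Say whether each participant contributed exactly one ulcer, and report the numbers of participants and of wounds per arm. If everyone had one ulcer, this is a change of wording and costs nothing.

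If any participant contributed more than one, there are two acceptable routes:
- Keep the wound-level outcome and analyse it with GEE or cluster-robust variance by participant, with the same clustering in the Cox model. The cost is a slightly larger standard error.
- Analyse one index ulcer per participant, chosen by a rule that uses baseline data only and is fixed without reference to results by arm. The cost is a smaller denominator.

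The opening section dates the conduct of the trial to January 2022 to June 2024 and the document to 29 May 2025, so data collection is complete. An index-ulcer analysis introduced now must be declared as specified after the fact. The clustered route avoids redefining the outcome. Either route uses data already collected and takes a few sentences in Outcomes and Data Collection and in Statistics.
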